# 3.5 Collection of Clinical Specimens

During the study will be collected 2 blood draws approximately at 13 and 24 months (Visit 5 and Visit 6). Detailed information about the laboratory assays is to be provided in section 7.0, Assessments.

Processing of each specimen should be completed by a qualified site member and in accordance with the study-specific Clinical Specimen Laboratory Manual. Testing of clinical specimens will be performed by a Novartis or designated laboratory. Refer to the study-specific Clinical Specimen Laboratory Manual for additional details.

### **Blood Specimens**

An approximately 5 mL sample of blood will be drawn from all subjects at visits 5 and 6; a 5 mL sample of blood will provide the necessary serum volume for the serology assays (approximately half of the blood draw volume). The blood volume will not exceed 5 mL at each time point.

The blood will be used for immunological assays See section 7.0, Assessments for additional details.

The total amount of blood collected over the study period per subject will be 10 mL.

# 3.6 Stopping/Pausing Guidelines

There are no predetermined stopping rules other than circumstances for which subjects may not be eligible for additional study vaccinations as described in section 4.0, Selection of Study Population or may be withdrawn from the study according to the best interests of the subject as described in section 3.8, Premature Withdrawal from Study.

### 3.7 Data Monitoring Committee

Not applicable for this study.

### 3.8 Premature Withdrawal from Study

Subjects may withdraw at any time, or be dropped from the study at the discretion of the investigator should any untoward effects occur and/or for safety reasons. In addition, a subject may be withdrawn by the investigator or the Sponsor if he/she violates the study plan or for administrative reasons. The investigator or study coordinator must notify the Sponsor immediately when a subject has been withdrawn due to an adverse event.

The circumstances above are referred to as premature withdrawal from the study, and the reason for premature withdrawal should be clearly documented and detailed in the source documentation. The investigator should make every attempt to evaluate the subject's safety, including resolution of ongoing AEs, at the time of premature withdrawal. If a subject wants to withdraw from the study before all doses are administered or prior to the last planned study visit, the subject will be asked to be followed for safety for the duration of the study. When a subject withdraws, or is withdrawn, from the study, the procedures described in section 5.5.1, Early Termination Visit should be completed if possible.

The reasons for premature withdrawal from the study include: adverse event, death, withdrawal of consent, lost to follow-up, administrative reason, and protocol deviation. These reasons are described in greater detail below.

#### **Adverse Event**

For any subject withdrawn from study participation prior to the planned Study Termination Visit, it is important to determine if an AE was associated with the reason for discontinuing the study. This AE must be identified on the AE CRF page by indicating "Withdrawn from study due to AE". Any ongoing AEs at the time of study withdrawal must be followed until resolution or stabilization.

Subjects who develop a serious adverse event (SAE) judged to be possibly or probably related to the study vaccine, including hypersensitivity reactions, should not receive subsequent vaccination.

PRO-01 TEMP 06 / Atlas No. 293620 Version No. 3 / Version Date: November 10, 2014

#### Death

For any subject withdrawn from study participation due to death, this should be noted on the Study Termination CRF page and the associated SAE that led to the death must be reported.

#### Withdrawal of consent

The subject parent(s)/legal guardian(s) can withdraw consent for participation in the study at any time without penalty or loss of benefit to which the subject is otherwise entitled. Reason for early termination should be deemed as "withdrawal of consent" if the subject withdraws from participation due to a non-medical reason (i.e., reason other than AE). If the subject parent(s)/legal guardian(s) intends to withdraw consent from the study, the investigator should clarify if the subject will withdraw completely from the study or if the subject will continue study participation for safety, or a subset of other study procedures. If the subject requests complete withdrawal from the study, no further study interventions will be performed with the subject.

#### Lost to Follow-Up

For subjects who fail to show up for final visits (clinic or telephone contacts), or for three consecutive visits, study staff are encouraged to make at least three documented attempts to contact the subject by telephone and at least one documented written attempt to contact the subject parent(s)/legal guardian(s) to encourage the completion of study termination procedures. These efforts to contact the subject should be recorded in the source document. The termination date for the subject to be captured on the Study Termination CRF page is the date of the last successful contact (clinic visit or telephone) with the subject.

#### Administrative Reason

Examples for subjects withdrawn from the study due to administrative reason can include: Sponsor decision to terminate the study, subject meeting a pre-specified withdrawal criterion, subject discontinuation for insurance issues, moving, no time, etc. This reason should be noted in the Study Termination CRF page and any ongoing AEs at the time of study withdrawal must be followed until resolution/stabilization.

If the clinical study is prematurely terminated by the Sponsor, the investigator is to promptly inform the study subjects and local EC/IRB and should assure appropriate therapy and follow up for the subjects. All procedures and requirements pertaining to the archiving of study documents should be followed. All other study materials (study medication/vaccines, etc.) must be returned to the Sponsor.

PRO-01 TEMP 06 / Atlas No. 293620 Version No. 3 / Version Date: November 10, 2014 For subjects who are withdrawn from the study due to receipt of an excluded medication/vaccination or due to significant protocol non-compliance, this reason should be noted in the Study Termination CRF page.

#### **Protocol Deviation**

A protocol deviation is any change, divergence, or departure from the study design or procedures of a study protocol. In general, subjects associated with protocol deviations may remain in the studyunless continuation in the study jeopardizes the subject's health, safety, or rights.

Investigators will apply due diligence to avoid protocol deviations. Under no circumstances should the investigator contact Novartis or its agents, if any, monitoring the study to request approval of a protocol deviation, as no authorized deviations are permitted. If the investigator feels a change to the protocol would improve the conduct of the study this must be considered a protocol amendment, and unless such an amendment is agreed upon by Novartis and approved by the IRB/EC and health authorities it cannot be implemented.

### 3.9 End of Study

Most clinical trials intended to support the efficacy/immunogenicity and safety of an Investigational Product proceed to full completion of planned sample size accrual.

Evaluation of the primary and/or secondary immunogenicity/efficacy objectives requires the testing of biological samples from the study subjects, which can only be completed after all samples are collected. The last samples for the analysis of the primary and/or secondary objectives will be taken at visit 6. For the purpose of this protocol, end of study is defined as the completion of the testing of such biological samples, to be achieved no later than 8 months after collection of the last biological sample visit 6.

#### 4.0 SELECTION OF STUDY POPULATION

#### 4.1 Inclusion Criteria

In order to participate in this study, all subjects must meet ALL of the inclusion criteria described.

- 1. Healthy male and female 2 month-old infants (55 89 days) on the day of consent.
- 2. Infants whose parents or legal guardians have voluntary given written informed consent after the nature of the study has been explained according to local regulatory requirements, prior to study entry.
- 3. Infants whose parents or legal guardians can comply with study procedures including follow-up

Prior to receipt of study vaccination, subjects must be evaluated to confirm that they are eligible for subsequent vaccination. If subjects do not meet any of the original inclusion criteria listed above, they should not receive additional vaccinations.

#### 4.2 Exclusion Criteria

Each subject must not have/have been:

- 1. previously received any meningococcal A, C, W and Y vaccines.
- 2. previous confirmed or suspected disease caused by *N. meningitidis* or who have had household contact with and/or intimate exposure to an individual with laboratory confirmed *N. meningitidis* infection at any time since birth.
- 3. progressive, unstable or uncontrolled clinical conditions.
- 4. a history of anaphylactic shock, asthma, urticaria or other allergic reaction after previous vaccinations or known hypersensitivity to any vaccine component, such as latex allergy.
- 5. experienced significant acute or chronic infection within the previous 7 days or have experienced fever (temperature  $\geq 38.0^{\circ}$ C [100.4°F]) within the previous 3 days.
- 6. any confirmed or suspected immunosuppressive or immunodeficient condition, based on medical history and physical examination.
- 7. received treatment with systemic administration corticosteroids (PO/IV/IM) for more than 14 consecutive days from birth.

- 8. ever received blood, blood products and/or plasma derivatives or any parenteral immunoglobulin preparation (including Hepatitis B immune globulin) at anytime since birth and for the full length of the study.
- 9. any bleeding disorder which is considered as a contraindication to intramuscular injection or blood draw.
- 10. any condition which, in the opinion of the investigator, might interfere with the results of the study or pose additional risk to the subject due to participation in the study.
- 11. received or are planning to receive any investigational or non-registered medicinal product from birth and throughout the study.
- 12. received oral or parenteral antibiotic treatment in the 3 days prior to the scheduled blood draw (topical antibiotics are acceptable, including antibiotic eye drops).
- 13. relatives of site research staff working on this study.

Prior to receipt of study vaccination, subjects must be evaluated to confirm that they are eligible for subsequent vaccination. At subsequent vaccinations, if subjects meet any of the original exclusion criteria listed above (with exception exclusion criteria 1, previous received the study vaccine), they should not receive additional vaccinations.

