# 4.3 Criteria for Delay of Vaccination

There may be instances when individuals meet all eligibility criteria for vaccination yet have a transient clinical circumstance which may warrant delay of vaccination:

- experienced significant acute or chronic infection within the previous 7 days or have experienced fever (temperature ≥ 38.0°C [100.4°F]) within the previous 3 days
- or use of antipyretics and/or analgesic medications within 24 hours prior to vaccination.

Under such circumstances, a subject may be considered eligible for study enrolment after the appropriate window for delay has passed and inclusion/exclusion criteria have been rechecked, and if the subject is confirmed to be eligible.

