### 5.2 Vaccination Clinic Visit(s)

Vaccination will be performed on day 1, day 61, day 121 and day 301. For studies which have visits for concomitant vaccinations or treatments, see section 6.5, Prior and Concomitant Medications and Vaccines for those visit procedures.

After completing the pre-vaccination procedures on day 1, administer the vaccine to the subject according to the procedures described in section 6.3, Vaccine Preparation and Administration. Prior to administration of each vaccination, confirm that the subject is eligible for additional study vaccinations and does not meet any criteria for delaying additional study vaccinations as described in section 4.0, Selection of Study Population.

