#### **Now Reads:**

There are clinical circumstances that warrant delay of blood collection for immunogenicity assessments in this study. These situations are listed below. In the event that a subject meets a criterion for delay of blood collection, blood collection may proceed once the window for delay has passed.

Subject has received oral or parenteral antibiotic treatment in the 7 days prior to the scheduled blood draw (topical antibiotics are acceptable, including antibiotic eye drops).

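### Protocol 4.2 read literally ends the vaccine series for a passing infection or fever that 4.3 treats only as a reason to delay

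*Protocol*

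**What the plan says.** Four parts of the protocol govern whether a child may receive dose 2, 3 or 4.

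- **Section 4.2, closing paragraph.** The exclusions are checked again before each later dose: "At subsequent vaccinations, if subjects meet any of the original exclusion criteria listed above". The sentence carries one exemption and then its consequence: "with exception exclusion criteria 1, previous received the study vaccine), they should not receive additional vaccinations". Criterion 5 in the same list covers a child who has "experienced significant acute or chronic infection within the previous 7 days or have experienced fever", with a 7-day limit for infection and a 3-day limit for fever.
- **Section 4.3.** The same infection and fever condition is the first reason to delay a dose. The section opens with "There may be instances when individuals meet all eligibility criteria for vaccination yet have a transient clinical circumstance which may warrant delay of vaccination" and closes by saying that "a subject may be considered eligible for study enrolment after the appropriate window for delay has passed" and the criteria have been rechecked.
- **Section 5.2.** Before each dose the site must "confirm that the subject is eligible for additional study vaccinations and does not meet any criteria for delaying additional study vaccinations", with a reference to section 4.0.
- **Section 6.3, precautions.** For the first dose it cites 4.1 and 4.2. For subsequent doses it cites only 4.3.

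Section 3.6 says there are no predetermined stopping rules, and excepts "circumstances for which subjects may not be eligible for additional study vaccinations as described in section 4.0" and withdrawal in the child's best interests under 3.8.

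**The concern.** For the same child on the same day, 4.2 says to give no more vaccine and 4.3 says to wait. A site that follows 4.2 to the letter stops the series for a fever that another site would wait out, and each can point to the protocol.

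Three things are at stake. The stopped child misses planned doses because of a passing illness. Sites may handle the same event differently. PPS membership then depends partly on which section a site read.

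**Working it through.** The plan gives no figure on this point, so the check is mainly a comparison of the texts.

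**Step 1: does 4.2 cover criterion 5 at later doses?** Yes. The rule reaches every listed exclusion and exempts only criterion 1. It has no step for delay, recheck or resumption, and it refers to further vaccinations in the plural, not only to the dose due that day.

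**Step 2: does 4.3 resolve the conflict?** Not as worded.

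- Its premise is a child who meets all eligibility criteria. A child with the listed infection or fever meets exclusion criterion 5, so the premise fails for the section's own first item.
- Its outcome is eligibility for enrolment. A child due dose 2, 3 or 4 is already enrolled, and no sentence says that the later dose may then be given.

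**Step 3: do 5.2 and 6.3 resolve it?** Only in part. Section 5.2 shows that delay was meant to apply to additional doses. But it sets two conditions: no delay criterion applies, and the child is eligible for additional vaccination. The second leads back to 4.2. Section 6.3 points to delay but leaves out 4.1 and 4.2. That is an incomplete cross-reference, because 4.1, 4.2, 5.2, 6.5 and the schedule of events require the rechecks anyway.

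**Step 4: did an amendment correct it?** No listed change does. Change 6 corrects the antibiotic interval. Change 7 adds a delay rule for blood draws to 4.3 and does state how to resume: "blood collection may proceed once the window for delay has passed". Nothing listed alters the exemption in 4.2, the vaccination sentence in 4.3, or 6.3.

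**Step 5: effect on the analysis sets (SAP section 7.7, Table 7.7-3).**

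| What happens at dose 2, 3 or 4 | Code | FAS | PPS Visits 5 and 6 |
|---|---|---|---|
| Series stopped (literal 4.2) | 140.4 | not excluded | excluded from both |
| Dose delayed, given in window | none | not excluded | not excluded |
| Dose delayed, given out of window | 260.2 to 260.4 | not excluded | excluded from both |

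**Step 6: how much can be bounded.**

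- Ceiling on later-dose checks: 135 children × 3 doses = 405. This counts checks, not affected children.
- Room to delay: Visits 2 and 3 close 7 days after target and Visit 4 closes 14 days after target. A visit booked on its target day can therefore be deferred by up to 7 or 14 days with the child still in both PPS sets.
- Assume that the 7-day or 3-day clock starts when the illness ends, and that the illness is still present on the target day. The days it may continue with the dose still in window are then the window minus the clock:

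| | Visits 2 and 3 | Visit 4 |
|---|---|---|
| Infection (7-day clock) | 7 − 7 = 0 | 14 − 7 = 7 |
| Fever (3-day clock) | 7 − 3 = 4 | 14 − 3 = 11 |

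Each figure is one day lower if the look-back period is counted strictly. At Visits 2 and 3, then, an infection still present on the target day leaves almost no room, even under the delay rule.

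**The case against.** The best answer is that the protocol, read as a whole, already means delay. Sections 5.2 and 6.3 both direct sites to the delay criteria for later doses. Section 4.3 deals specifically with this condition, and a specific rule normally governs a general one. Criterion 5 lapses by its own time limits, so a child who meets it today need not meet it next week, and 4.2 does not say that the bar is permanent. Section 3.6 refers to all of section 4.0 and favours neither reading. Finally, only a sensitivity set could change, and only if a site takes the unintended reading.

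Much of this stands. Delay is the likely intent, 3.6 does not settle the matter, and the consequence is small. It does not remove the conflict, however. Section 5.2 still requires eligibility, which leads back to 4.2, and 4.3 never states that a later dose may proceed. Sites have to infer what the blood-draw rule says outright.

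One limit also stands. The full protocol text available is Version 1, with later changes shown only as a log. The amended 4.3 cannot be read as a whole, so the statement about amendments applies to the listed changes.

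**Conclusion.** The concern holds, as a minor inconsistency between operative rules. Section 4.2 as written ends the series for a condition that 4.3 would only delay, and no listed change reconciles them.

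For one affected child, the literal rule means an incomplete series and loss from both PPS sets. The delay rule keeps the child in both if the dose is given in window. FAS membership, on which the descriptive primary analysis rests, is unaffected by any of the codes involved.

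The number of children affected cannot be derived, because the documents give neither an illness rate nor any indication of how sites would read 4.2. The text conflict needs no numerical assumption. Only the tolerance for continuing illness in Step 6 does, namely that the clock starts when the illness ends.

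**What to change.** Three sentences in a protocol amendment:

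1. **Section 4.2, closing paragraph.** Add criterion 5 to the exemption and refer it to 4.3: delay, recheck, then vaccinate.
2. **Section 4.3.** Cover both enrolment and each later dose, and drop the premise that the child meets all eligibility criteria. End it as the blood-draw rule ends: vaccination may go ahead once the delay period is over and the criteria have been rechecked.
3. **Section 6.3.** Cite 4.1, 4.2 and 4.3 for subsequent doses.

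Neither data collection nor the SAP changes.

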# 4.3 Criteria for Delay of Vaccination

There may be instances when individuals meet all eligibility criteria for vaccination yet have a transient clinical circumstance which may warrant delay of vaccination:

- experienced significant acute or chronic infection within the previous 7 days or have experienced fever (temperature ≥ 38.0°C [100.4°F]) within the previous 3 days
- or use of antipyretics and/or analgesic medications within 24 hours prior to vaccination.

Under such circumstances, a subject may be considered eligible for study enrolment after the appropriate window for delay has passed and inclusion/exclusion criteria have been rechecked, and if the subject is confirmed to be eligible.

#### 5.0 STUDY PROCEDURES

The sections that follow provide an overview of the procedures that are to be followed in enrolling, evaluating, and following subjects who participate in this clinical study. Visits can be either clinic visits or safety follow-up telephone calls, as specified in the Table below and in the Time and Events Table.

**Table 5.0-1 Study Procedures** 

Visit Category	Procedures
Pre-vaccination Clinic Visit(s)	Section 5.1. describes procedures to be followed prior to study vaccination: informed consent/assent, screening, enrolment, and randomization
Vaccination Clinic Visit(s)	Section 5.2 describes procedures to be followed during each clinic visit involving vaccination: vaccination, post-vaccination procedures, and post-vaccination reminder calls
Post-vaccination Visit(s)	Section 5.3 describes follow-up clinic visits and safety follow-up calls
Unscheduled Visit(s)	Section 5.4 describes possible procedures to be followed at unscheduled clinic visit
Study Termination Visit	Section 5.5 describes procedures to be followed at the last study visit for a subject (may include early termination visit)

## 5.1 Pre-vaccination Clinic Visit(s)

This section describes the procedures that must be performed for each potential subject prior to vaccination, including obtaining informed consent/assent, screening, enrolment and randomization.

#### 5.1.1 Informed Consent/Assent

"Informed consent" is the voluntary agreement of an individual or his/her legal guardian(s) to participate in research. Consent must be given with free will of choice, and without undue inducement. The individual must have sufficient knowledge and understanding of the nature of the proposed research, the anticipated risks and potential benefits, and the requirements of the research to be able to make an informed decision.

Informed consent following local IRB/EC guidance **must** be obtained before conducting any study-specific procedure (i.e., all of the procedures described in the protocol). The

process of obtaining informed consent should be documented in the subject source document in addition to maintaining a copy of the signed and dated informed consent.

Informed consent of the parent(s)/legal guardian(s) and assent of subject following local IRB/EC guidance **must** be obtained before conducting any study-specific procedures (i.e., all of the procedures described in the protocol). The process of obtaining informed consent and assent should be documented in the subject source document in addition to maintaining a copy of the signed and dated informed consent. Additional specifics regarding the informed consent and assent processes are located in section 13.2, Informed Consent Procedures.

If a subject parent(s)/legal guardian(s) is unable to read, an impartial witness should be present during the entire informed consent discussion. An impartial witness is defined as a person who is independent from study conduct, who cannot be unfairly influenced by those involved with the study, who attends the informed consent process if the subject or the subject's legally acceptable representative cannot read, and who reads the informed consent form and any other written information supplied to the subject. After the written informed consent form and any other written information to be provided to subjects, is read and explained to the subject parent(s)/legal guardian(s) and after the subject parent(s)/legal guardian(s) has verbally consented to the subject's participation in the study and, if capable of doing so, has signed and personally dated the informed consent form, the witness should sign and personally date the consent form. By signing the consent form, the witness attests that the information in the consent form and any other written information was accurately explained to, and apparently understood by, the subject parent(s)/legal guardian(s) and that informed consent was freely given by the subject parent(s)/legal guardian(s).

